### Global assessment of host response by whole blood transcriptomics on PAXgene RNA

The global host response will be evaluated by whole blood transcriptomic profiling (RNA-Seq) in order to identify predictors of impaired vaccine take by correlating the baseline transcriptomic profile on the day of vaccination with peak immune response at 3-6 weeks. HLA-typing will also be undertaken, where consent is provided, in order to assess how an individuals HLA-type may affect the immune response to the vaccine.

## Reporting

The data manager will receive results for assays in form of an Excel table – one signed hard copy and one electronic copy, by email.

### 6.4.1 HANDLING OF RESIDUAL SAMPLES ON COMPLETION OF TESTING

During the consent process, parents/guardians will be asked for consent to keep their child's residual samples (if any) to be used for further research to improve understanding of vaccines and how they work. Lack of consent to this will not preclude participation in the study. Where consent is given, any residual samples will be archived at -70 °C or below at PHE Colindale. Residual samples from participants who do not give such consent will be destroyed.

## 6.5 TRIAL CLOSURE

The expected study duration is ~1 months for any individual participant.

The study will be considered complete following enrolment of the last patient and completion of all study procedures in that patient.

No interim analyses are planned.

## 6.6 EXPENSES AND PAYMENTS

We will aim to perform study interventions at the same time as an existing clinic appointment. It is therefore not expected that the participants or their families will incur any additional costs requiring reimbursement for the first visit.

We will offer up to £25 towards receipted travel expenses for additional study visits. We will also offer participants a £20 cinema voucher (approximately equivalent to the cost of one adult and one child cinema ticket in London) as a small token of thanks, at the second study visit.

## 7 ADVERSE EVENT REPORTING

### 7.1 DEFINITIONS

**Adverse Event (AE):** any untoward medical occurrence in a patient or clinical trial subject administered a medicinal product and which does not necessarily have a causal relationship with this treatment. *An AE can therefore be any unfavourable and unintended sign (including an abnormal laboratory finding), symptom, or disease temporally associated with the use of an investigational medicinal product (IMP), whether or not considered related to the IMP.*

An adverse event will be followed until it resolves or until 30 days after a participant terminates from the study, whichever comes first.

**Adverse Reaction (AR):** all untoward and unintended responses to an IMP related to any dose administered. *All AEs judged by either the reporting investigator or the sponsor as having reasonable causal relationship to a medicinal product qualify as adverse reactions. The expression reasonable causal relationship means to convey in general that there is evidence or argument to suggest a causal relationship.*

**Unexpected Adverse Reaction:** an AR, the nature or severity of which is not consistent with the applicable product information (eg summary of product characteristics (SmPC) for an authorised product). *When the outcome of the adverse reaction is not consistent with the applicable product information this adverse reaction should be considered as unexpected. Side effects documented in the SmPC which occur in a more severe form than anticipated are also considered to be unexpected.*

**Serious Adverse Event (SAE) or Serious Adverse Reaction:** any untoward medical occurrence or effect that:

- **Results in death**
- **Is life-threatening** – *refers to an event in which the subject was at risk of death at the time of the event; it does not refer to an event which hypothetically might have caused death if it were more severe*
- **Requires hospitalisation, or prolongation of existing inpatients' hospitalisation**
- **Results in persistent or significant disability or incapacity**
- **Is a congenital anomaly or birth defect**

Medical judgement should be exercised in deciding whether an AE/AR is serious in other situations. Important AE/ARs that are not immediately life-threatening or do not result in death or hospitalisation but may jeopardise the subject or may require intervention to prevent one of the other outcomes listed in the definition above, should also be considered serious.

**Suspected Unexpected Serious Adverse Reaction (SUSAR):** any suspected adverse reaction related to an IMP that is both unexpected and serious.

### 7.1.1 DOCUMENTATION OF ADVERSE EVENTS

For the purposes of this study, parent/carers will be asked to inform the study team of any adverse events occurring up to the time that the Day 8 swab is collected, by completing the relevant section on the daily swab return form. All serious adverse events (SAEs) or reactions (SARs) will be reported on a SAE report form, for 28 days from after LAIV administration, regardless of their severity or relation to study medication or study procedure. The investigator will treat participants experiencing adverse events appropriately and observe them at suitable intervals until their symptoms resolve or their status stabilizes.

SAEs will be reported within 24 hours of the Site Study Team becoming aware of the event. All SUSARs will be reported by the CI to the relevant Competent Authority, Sponsor, REC and other parties, as applicable. For fatal and life-threatening SUSARs, this will be done no later than 7 calendar days after the Sponsor or delegate is first aware of the reaction. Any additional relevant information will be reported within 8 calendar days of the initial report. All other SUSARs will be reported within 15 calendar days. All SAE information must be recorded on an SAE form and emailed to the JRCO ([[contact]](mailto:[contact])).

SARs will also be reported to MHRA through the yellow card system.

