## 6 STUDY VISITS & PROCEDURES

The study schedule is summarised in the following flow chart and table:

	Visit 1	Days 1,2,3,4,5,6,7,8	Visit 2 - Day 28 (window D21-42)
Written Informed Consent (parent/guardian)	x		
Written assent (child)	x		
Medical assessment	x		
Urine pregnancy test (if pregnancy cannot be excluded by clinical history alone)	x		
Vaccine administration followed by 20 mins observation	x		
Nasal swab and adverse event form	x	x (at home)	x
Oral fluid collection	x		x
Blood test	x §		x
2 nd dose in children <9 years who meet DoH criteria (see 6.1.3)			(x)

§baseline blood sample may be collected up to 2 months before vaccination, if the study participant is having a blood test for another reason and informed consent has been obtained already.

Both study visits will be carried out by members of the research team as per the above schedule, and appointment windows. If any SAE is reported, this will be documented following routine procedures. All clinical information and agreement with parents to be documented in CRFs.

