### 6.1 STUDY VISITS / HOME INTERVENTIONS

#### 6.1.1 VISIT 1 - DAY 0

- Answer any questions the family has about the study having read the PIL.
- Obtain written informed consent from the parent/guardian
- Obtain written assent from child
- Verify inclusion and exclusion criteria with the parent/ guardian (if any notes need to be checked this would be done after consent)
- If the child meets all the inclusion criteria and none of the exclusion criteria, enrol in the study and allocate the next sequential unique participant study number.
- Measure and record body temperature
- *Collect baseline blood sample (up to 25ml). Participants will be offered local anaesthetic cream (to be applied 30mins prior to venepuncture) to minimise discomfort.§*
- Take the initial nasal swab, demonstrating to parents how this is done to facilitate compliance with taking the nasal swabs at home in the 8 days following vaccination.
- Administer LAIV according to prescription chart, and record this on CRF and chart, including batch number and expiry.
- Observe for 20 minutes, during which time collect oral fluid sample. Also confirm parent has understood how to take the nasal swabs, including posting back to team.
- Record vaccination details via the medical records system.
- Ask parent/ guardian to notify study team of any serious adverse events/reactions
- Arrange further visit for 3-6 weeks following vaccination.

§baseline blood sample may be collected up to 2 months before vaccination, if the study participant is having a blood test for another reason and informed consent has been obtained already.

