### 6.1.3 VISIT 2 - DAY 28 (WINDOW DAY 21 TO DAY 42) FOLLOWING VACCINATION

- Confirm continued consent with parent/ guardian and note continuation on GP notes and CRF (if consent withdrawn, complete a withdrawal form documenting this).
- Obtain interim history, specifically any serious adverse events, serious reactions, and visits to hospital – report SAEs according to section 7 below.
- Take nasal swab (same as initial swab)
- Collect oral fluid sample
- Collect a blood sample (up to 25ml). Participants will be offered local anaesthetic cream (to be applied 30mins prior to venepuncture) to minimise discomfort.
- 2nd dose of LAIV were indicated:

Children who meet DoH criteria for specified 'clinical risk categories' (Table 1) and are under 9 years of age and have not received prior seasonal influenza vaccination will also be offered a second dose of LAIV. We expect very few children to meet this criteria, as most would have received prior influenza vaccination. However, there is a duty of care to our participants and we are therefore including provision for a second dose in this protocol.

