### 7.3.1 NON SERIOUS AR/AES

[figure not shown]
All such events, whether expected or not, should be recorded on the daily swab return forms completed by parents. Non-serious AR/AEs will be collected only where they occur within 8 days of vaccination. Adverse events will then be collated and reported to the study CI within one month of occurrence.

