### 7.3.2 SERIOUS AR/AES

All SAEs and SUSARs should be reported on the day of occurrence, where these occur within 28 days of vaccination. The SAE form asks for nature of event, date of onset, severity, corrective therapies given, outcome and causality (i.e. unrelated, unlikely, possible, probably, definitely). The responsible investigator should sign the causality of the event. Additional information should be sent to the CI within 5 days if the reaction has not resolved at the time of reporting. Any expected SAR will also be reported via the MHRA yellow card system.

**SAEs:** An SAE/SUSAR form should be completed and emailed to the study CI immediately, who will in turn inform the JRCO (email to [[contact]](mailto:[contact])) within 24 hours.

**SUSARs:** All SUSARs will be reported by the CI to the relevant Competent Authority (MHRA) and to the REC and other parties as applicable. For fatal and life-threatening SUSARs, this will be done no later than 7 calendar days after the Sponsor or delegate is first aware of the reaction. Any additional relevant information will be reported within 8 calendar days of the initial report. All other SUSARs will be reported within 15 calendar days.

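### SAEs are reportable for 28 days, but the only scheduled SAE enquiry after Day 8 falls anywhere from day 21 to day 42: early visits leave a short tail to unprompted reports, and late visits put their own blood draw outside the period

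*Combined protocol and SAP*

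**What the plan says.** **Reporting period.** Section 7.1.1 requires SAEs and serious reactions to be reported "for 28 days from after LAIV administration, regardless of their severity or relation to study medication or study procedure". Section 7.3.2 agrees: "All SAEs and SUSARs should be reported on the day of occurrence, where these occur within 28 days of vaccination".

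**Visit 2.** The heading of section 6.1.3 is "VISIT 2 - DAY 28 (WINDOW DAY 21 TO DAY 42) FOLLOWING VACCINATION", and the Visit 1 list in 6.1.1 says "Arrange further visit for 3-6 weeks following vaccination". At Visit 2 staff are to "Obtain interim history, specifically any serious adverse events, serious reactions, and visits to hospital" and to report SAEs under section 7. The same visit includes venepuncture of up to 25 ml and, for a small subgroup, the offer of a second LAIV dose.

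**Other routes for safety information.** At Visit 1 parents are asked to tell the team about serious events, with no end date (6.1.1). Parents also complete an adverse event form with each daily swab up to Day 8 (6.1.2, 7.1.1). No further contact is described between the Day 8 form and Visit 2, or after Visit 2.

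**Related wording.** The schedule table in section 6 has a row "Nasal swab and adverse event form" that is marked at Visit 2, while 7.3.1 states "Non-serious AR/AEs will be collected only where they occur within 8 days of vaccination". Section 7.1 says "An adverse event will be followed until it resolves or until 30 days after a participant terminates from the study, whichever comes first". Section 7.1.1 has the investigator observe events until they resolve or stabilise, and 4.3 says the same for withdrawals due to an adverse event. Neither gives the 30-day limit.

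**The concern.** The reporting period is fixed from vaccination, but the enquiry that would find most late events moves with the appointment. Take two children, each admitted to hospital on day 25. The child seen on day 28 is asked directly about hospital visits. The child seen on day 21 has already had the last scheduled contact, and the admission is recorded only if the parent thinks to call.

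At the other end of the window, a child seen on day 35 has a study venepuncture one week after SAE reporting has closed. Section 7.1.1 makes relation to a study procedure no bar to reporting, yet a serious complication of that blood draw would have no reporting rule to fall under. Section 6.1.3 sends staff to section 7 for whatever the history reveals, and section 7 does not mention events on days 29-42.

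What is at stake is evenness of SAE ascertainment and a clear instruction for staff. The primary shedding analysis is not affected.

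**Working it through.** The documents give no figure of their own on this point, so the check is a count of days.

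**Inputs.** SAE period: 28 days after LAIV (7.1.1, 7.3.2). Visit 2 window: days 21 to 42 (section 6 table, 6.1.3). The 3-6 weeks in 6.1.1 agree, since 3 x 7 = 21 and 6 x 7 = 42. Last daily form: Day 8 (6.1.2, 7.1.1). Children: 30 (section 3).

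**Step 1. The window against the period.** Permitted Visit 2 days: 42 - 21 + 1 = 22.

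| Visit 2 on | Permitted days | Reportable days after the visit (28 - visit day) | Position of the blood draw |
|---|---|---|---|
| days 21-27 | 7 | 7 down to 1 | inside the period |
| day 28 | 1 | 0 | last day of the period |
| days 29-42 | 14 | 0 | 1 to 14 days outside |

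The longest tail is 28 - 21 = 7 days, or 7/28 = 25% of the period for that child. Visits on day 28 or later cover the full 28 days retrospectively. Even at a day-28 visit, a complication that starts the next day is outside the period.

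**Step 2. Interval without scheduled enquiry.** From the Day 8 form to Visit 2 is 21 - 8 = 13 days at the shortest and 42 - 8 = 34 days at the longest. Late visits are complete in coverage but rely on longer recall.

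**Step 3. Size of the early-visit tail.** The documents do not give the distribution of visit days. If visits were spread evenly over the 22 days (assumption), the mean tail is (7+6+5+4+3+2+1)/22 = 28/22 = 1.27 days per child, and the share of reportable child-days is 28/(22 x 28) = 28/616 = 4.5%. The bounds are 0% if every visit is on day 28 or later and 25% if every visit is on day 21.

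**Step 4. Expected events in the tail.** Assume an SAE risk of 1% to 5% per child over 28 days, spread evenly in time; the documents give no figure. With the 4.5% share (28/616):

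- 1%: 30 x 0.01 x 28/616 = 0.014 events
- 5%: 30 x 0.05 x 28/616 = 0.068 events

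If every child were seen on day 21, the range is 30 x 0.01 x 0.25 = 0.075 to 30 x 0.05 x 0.25 = 0.375 events. All four figures are before any notification by parents, so they are upper limits on what would be missed under each assumption.

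**Step 5. Second dose.** A second dose, where offered, is given at Visit 2, and the documents describe no visit after it. Sections 7.1.1 and 7.3.2 count 28 days from LAIV or vaccination without saying whether a second dose starts a new count.

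**The case against.** The best counter-argument is that the plan does not rely on Visit 2 alone. Parents are asked at Visit 1 to report serious events and complete daily forms to Day 8, and nothing in section 7 ends the duty to report at an early Visit 2. An SAE on day 25 remains reportable whether or not anyone asks. This stands. A reader might infer that Visit 2 is the only planned SAE enquiry, or that a child seen on day 21 has left SAE reporting; the documents support neither. What remains is that, after Day 8, Visit 2 is the only scheduled *active* enquiry. The parent leaflet and the swab return form are not in the documents, and the reporting flowchart that section 7.3 mentions is not shown, so what parents are told about later contact cannot be fully judged.

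A reader might also infer that staff face contradictory rules for late visits. That goes too far: a history that is wider than the reporting period is not a contradiction, and a late visit does cover all 28 days. The gap is narrower. The visit's own procedures fall after the period, and section 7 is silent on them.

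It is tempting, too, to turn the day counts into proportions of children: 7/22 = 32% with an early visit and 14/22 = 64% with a late one. Those hold only if visits are spread evenly. Visit 2 is nominally day 28, and nothing in the documents supports an even spread.

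Finally, sections 9 and 9.1 define no safety endpoint and no safety analysis, and this is a single-arm study of 30 children receiving an approved vaccine. That stands as well and limits the consequence. It does not remove the protocol's own reporting duty.

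On the secondary wording, the Visit 2 mark in the schedule table may refer only to the swab, because the row combines two items. That is a reason to clarify the table, not evidence of an error in safety collection.

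**Conclusion.** The point holds in a limited form. The 28-day SAE period and the day 21-42 window for the one scheduled enquiry after Day 8 do not line up. For visits on days 21-27, the last 1 to 7 reportable days rest on unprompted notification by parents. For visits on days 29-42, the venepuncture lies 1 to 14 days outside the reporting period. Incomplete active ascertainment affects the early visits only.

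The numerical effect is small: about 4.5% of reportable child-days under an even spread, with bounds of 0% and 25%, and well under one expected event in the whole study at the assumed risks of 1% to 5%. These sizes rest on the assumed visit distribution and SAE risk; the mismatch itself rests only on the text. The case for acting is that the remedy is cheap and gives staff a clear rule, not that any result would change.

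**What to change.** 1. In 7.1.1 and 7.3.2, state that SAE reporting runs at least to day 28 and also covers SAEs related to Visit 2 procedures whenever that visit takes place, including events that emerge after it, for a short period that the sponsor specifies. Closing the period at the end of Visit 2 would not be enough, because a complication of a late blood draw may appear afterwards.
2. For children seen on days 21-27, send one closing text or email on day 28, through the reminder channel already used for the swabs (6.1.2), asking about serious events and hospital visits.
3. Reconcile 7.1.1 and 7.3.2 with the second dose in 6.1.3: state how the 28-day period applies to a dose given at Visit 2, so that the new wording does not shorten it. The rule is for the sponsor to set.
4. Reconcile two secondary items: the adverse event form marked at Visit 2 in the section 6 table against 7.1.1 and 7.3.1, and the end of event follow-up in 7.1 against 4.3 and 7.1.1.

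The cost is a wording amendment, one message per early attender, and possibly a few more SAE forms.

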### 7.2 GRADING AND ATTRIBUTION OF ADVERSE EVENTS

The study site will grade the severity of adverse events experienced by study participants according to the criteria set forth in the NCI-CTCAE Version 3.0

([http://ctep.cancer.gov/protocolDevelopment/electronic\\_applications/docs/ctcae3.pdf](http://ctep.cancer.gov/protocolDevelopment/electronic_applications/docs/ctcae3.pdf)).

This document provides a common language to describe levels of severity, to analyse and interpret data, and to articulate the clinical significance of all adverse events.

Adverse events will be graded on a scale from 1 to 5 according to the following standards in the NCI-CTCAE manual:

Grade 1 = mild adverse event.

Grade 2 = moderate adverse event.

Grade 3 = severe and undesirable adverse event.

Grade 4 = life-threatening or disabling adverse event.

Grade 5 = death.

All adverse events will be recorded and graded whether they are or are not related to disease progression or treatment. The NCI-CTCAE grades will be the primary source for scoring.

The relation, or attribution, of an adverse event to study participation will be determined by the investigator and recorded on CRF and/or SAE reporting form. The assignment of the causality should be made by the investigator responsible for the care of the participant using the definitions in the table below (Table 2), and with reference to the Reference Safety Information included in section 4.8 of the Summary of Product Characteristics. In the case of discrepant views on causality between the investigator and others, all parties will discuss the case. In the event that no agreement is made relating to a SUSAR, the MHRA will be informed of both points of view.

Relationship	Description
Unrelated	There is no evidence of any causal relationship
Unlikely	There is little evidence to suggest there is a causal relationship (e.g. the event did not occur within a reasonable time after administration of the trial medication). There is another reasonable explanation for the event (e.g. the participant's clinical condition, other concomitant treatment).
Possible	There is some evidence to suggest a causal relationship (e.g. because the event occurs within a reasonable time after administration of the trial medication). However, the influence of other factors may have contributed to the event (e.g. the participant's clinical condition, other concomitant treatments).
Probable	There is evidence to suggest a causal relationship and the influence of other factors is unlikely.
Definitely	There is clear evidence to suggest a causal relationship and other possible contributing factors can be ruled out.
Not assessable	There is insufficient or incomplete evidence to make a clinical judgement of the causal relationship.

**Table 2: Assignment of causality for adverse events**

## 7.3 REPORTING PROCEDURES

All adverse events should be reported. Depending on the nature of the event the reporting procedures below should be followed. Any questions concerning adverse event reporting should be directed to the study coordination centre in the first instance. A flowchart is given below to aid in the reporting procedures.

### 7.3.1 NON SERIOUS AR/AES

[figure not shown]
All such events, whether expected or not, should be recorded on the daily swab return forms completed by parents. Non-serious AR/AEs will be collected only where they occur within 8 days of vaccination. Adverse events will then be collated and reported to the study CI within one month of occurrence.

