### 6.1.2 DAILY HOME SWABS - DAYS 1-8

Parents will be asked to take daily nasal swabs from their child/young person at home, in the week following vaccination, from Day 1 until Day 8 post vaccination. The nasal swab, which looks like a large cotton bud, will be passed into the nostril and moved around for a minute. Parents will be provided with eight test kits, full instructions and Royal-Mail approved postage kits (for Category B specimens) and prepaid envelopes for each child, for posting back to PHE through the normal Royal Mail network.

Parents will be shown the process by their study nurse at the vaccination visit. Parents will receive a daily reminder text/email to take and post the samples. In the event of a missed swab, families will be asked to take the swabs as planned the next day. The final Day 8 swab can be collected up to 24 hours late i.e. on Day 9.

Adverse event information will be collected on a daily basis, using the form parents are asked to complete when they return the daily swabs to Public Health England.

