### 6.3.3 POSTING SAMPLES

Appropriate prepaid postage packs will be provided to parents to return **nasal swabs** on the day each is taken. Samples will be sent by Royal Mail to the Influenza Laboratory, Public Health England (PHE Colindale). **Oral fluid samples** will be sent directly to PHE by the research team.

All samples to be sent to PHE will be placed into a NOAX green topped tube containing an absorbent strip and then placed in an approved transport box (along with Sample Postage and Receipt Form CTD014). The box is then placed into a postage bag showing the “UN3373 biological substance, category B” identification diamond sticker, and either dropped at a post office or into a post box for delivery to the Influenza Laboratory, PHE Colindale.

**Blood samples:** Lithium heparin samples and PAXgene tubes will be transferred to the [name] laboratory at Imperial College London within 4 hours of collection. Serum will be separated from clotted blood following centrifugation, aliquoted and stored at -80°C until transfer on dry ice to the Influenza Laboratory, Public Health England (PHE Colindale) for further analysis.

Documentation included will identify the child by subject number and will allow documentation and tracking of the movement of samples between sites and laboratories (ref study SOPs). Logs of samples sent and received will be kept at PHE Colindale, to enable the identification of any lost or delayed samples and to provide a log of where samples are currently stored.

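### Parent-completed adverse event forms go to PHE with no stated step for prompt screening by the site, and sections 7.1.1 and 7.3.2 set different SAE reporting clocks

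*Combined protocol and SAP*

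**What the plan says.** Section 7.1.1 has parents tell the study team about adverse events up to the Day 8 swab "by completing the relevant section on the daily swab return form". Section 6.1.2 describes the same daily collection as "using the form parents are asked to complete when they return the daily swabs to Public Health England". Section 6.3.3 sends the swabs by Royal Mail to the PHE influenza laboratory, on the day each is taken.

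Section 7.3.1, headed as covering non-serious events, gives the onward step: "Adverse events will then be collated and reported to the study CI within one month of occurrence".

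Other sections place duties on the hospital side. Under section 7.1.1, "The investigator will treat participants experiencing adverse events appropriately and observe them at suitable intervals until their symptoms resolve or their status stabilizes". Section 7.2 has the study site grade severity and the investigator caring for the child assign causality. Section 7.1 asks for medical judgement on events that meet none of the listed seriousness criteria but "may jeopardise the subject or may require intervention to prevent one of the other outcomes listed".

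Serious events have their own route. At Visit 1 parents are asked to notify the study team of them (section 6.1.1), the SAE form is emailed to the chief investigator at once (section 7.3.2), and Visit 2 takes a history of serious events and hospital visits (section 6.1.3). Two reporting times are given. Section 7.1.1: "SAEs will be reported within 24 hours of the Site Study Team becoming aware of the event". Section 7.3.2: "All SAEs and SUSARs should be reported on the day of occurrence, where these occur within 28 days of vaccination".

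**The concern.** The form is the daily safety record for the home period, but it is addressed to a laboratory. The people who must grade, attribute and follow up what it contains are at the hospital. The faster SAE route starts only once somebody has recognised the event as serious, and during the home period that person is the parent. The category in section 7.1 that depends on medical judgement is the one a parent is least well placed to apply.

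At stake is a delay for a particular kind of event: one that a clinician might class as serious, that the parent does not, and that appears only on the posted form. Such an event could be assessed after it has resolved or worsened, and any SAE or SUSAR report arising from it would be late.

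The two SAE clocks are a separate matter. Staff cannot tell which one governs, and one of them runs from a time at which the team may know nothing of the event.

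**Working it through.** The plan states no figure to reproduce here. The check sets the sections side by side and adds calendar arithmetic.

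1. **Path of the form.** Parent completes it (7.1.1); it goes with the swab to PHE (6.1.2, 6.3.3); events are collated and reported to the chief investigator within a month (7.3.1). No visible text says who at PHE reads a form on arrival, whether it is screened for seriousness, or when it reaches the hospital team. Section 8.2 has a hospital team member verify clinical data electronically, but to find errors and omissions and with no deadline.

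2. **Who sorts serious from non-serious.** Section 7.3.1 applies to non-serious events and 7.3.2 to serious ones. For a home event, the first sorting is the parent's decision whether to contact the team directly as well as fill in the form. No clinician is required to look before the one-month limit.

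3. **Latest day for the chief investigator to have the report.** Latest day = day of event + one month, taking a month as 28 to 31 days.
   - Day 1 event: 1 + 28 = 29 to 1 + 31 = 32.
   - Day 8 event: 8 + 28 = 36 to 8 + 31 = 39.

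   Both ranges lie after the nominal Day 28 visit, though inside the Visit 2 window of day 21 to 42.

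4. **Visit 2 as a backstop.** Delay = day of visit − day of event. Shortest: 21 − 8 = 13 days. Longest: 42 − 1 = 41 days. Section 6.1.3 directs the history at serious events and hospital visits; the section 6 schedule also lists an adverse event form at that visit.

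5. **The two SAE clocks.**
   - Section 7.1.1 starts at awareness by the Site Study Team and allows 24 hours.
   - Section 7.3.2 starts at occurrence and allows the same day.

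   A form posted on the day of the swab will not normally be read at PHE that day. An event recalled at Visit 2 meets the second clock only if it happened on the day of the visit. For these events the first clock can be met and the second cannot. Whether receipt at PHE counts as awareness is not stated, and the term Site Study Team is not defined.

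**The case against.** A reader might infer that the clinician cannot act in time, or that no clinician ever sees the form. The documents do not support either. The one-month sentence covers non-serious events and is a maximum, not the expected delay. It ends with a report to the chief investigator, and section 7.2 has the site grade events. Nothing bars earlier transfer, and section 7.1.1 plainly intends the study team to be informed and the investigator to respond.

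A reader might also set one month against 24 hours as a measure of the delay. That compares limits for different classes of event. Nor does late arrival take an event outside SAE reporting: the 28 days in section 7.3.2 govern when it occurs, not when it is learned of.

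Other points on that side carry weight. The vaccine is licensed and dispensed as standard of care in what section 5.5 calls a type A Phase IV study, so slower collation of non-serious events is a proportionate choice. That PHE lies outside the Site Study Team is an inference. The flowchart mentioned in section 7.3, the text directly after section 7.3.2, and the parent instructions cited in section 6.3.1 were not available to this review, and any of them may give further routing. Their absence from the copy read is not evidence of a gap.

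These points limit the concern to events whose seriousness the parent does not recognise, and they lower confidence. They do not supply a screening step in sections 6.1.2, 7.1.1 or 7.3.1, and they do not reconcile the two SAE clocks.

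**Conclusion.** The point holds in a limited form. On the visible text, an event on days 1 to 8 that needs medical judgement to be recognised as serious, and that the parent enters only on the form, is not assured of timely review by the site and investigator responsible for it. The stated outer limit is about four weeks to one month after the event; Visit 2 may come sooner, but no earlier than 13 days after a day 8 event. The documents give no event rate, so the number of children affected cannot be estimated, and with at most 30 enrolled it may be none.

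The mismatch between sections 7.1.1 and 7.3.2 is plain in the text and does not depend on how the forms are routed.

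Confidence in the routing point is moderate. It assumes that PHE receipt is not already treated as site awareness and that the unseen flowchart and parent instructions add no forwarding step. The change is worth making because it is cheap and bears on safety oversight; it does not affect the shedding or immunogenicity analyses.

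**What to change.** - **Sections 6.1.2 and 7.3.1:** have PHE forward any form with an adverse event entry to the St Mary's team on the day it is opened, and have that team screen it for seriousness on receipt. Keep the one-month limit only for collated summaries to the chief investigator.
- **Sections 7.1.1 and 7.3.2:** reconcile the two SAE times into a single clock that starts at awareness, and state whether receipt at PHE counts as awareness.
- **Section 7.3 flowchart:** check it, and the parent instructions, against the revised wording.

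The cost is a wording amendment plus a small amount of forwarding and review for at most 30 children. Postal time and any wait before a pack is opened remain, so the Visit 1 request that parents notify the team directly of serious events should stay.
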